### **3 STUDY IMPLEMENTATION**

#### **3.1 STUDY DESIGN**

Calcitriol (half-life is 5-8 hour) and phosphorous will be withheld for 3 days prior to the initiation of BGJ398 to allow for washout.

After initiation of study drug, subject will complete 24 weeks of BGJ398 with escalation/de-escalation of drug as described in Sections 3.1.2 and 3.3. Patients will return to the NIH every 4 weeks while on BGJ398 for an outpatient visit and labs per the schedule of events. Between monthly NIH visits, labs will be obtained per the schedule of events at the patients' local laboratories and results will be forwarded to the study team for review. In addition, any patient taking a concomitant medication associated with prolonged QT will obtain an EKG as an outpatient within 7-10 days after an increase in BGJ398 or the relevant concomitant medication. At the end of 24th week of BGJ398 treatment, subjects will be admitted as inpatients at the NIH for detailed laboratory and imaging evaluation as described in schedule of events. At the completion of the 24 weeks of treatment, patients who appear to have had a complete metabolic response will be evaluated at the NIH every 4 weeks for 3 additional visits. Complete metabolic response will be defined as normalization of blood phosphate and FGF23 levels after withdrawal of study drug. Local labs will be obtained in between NIH visits as clinically indicated on an as-needed basis. Subjects who have normal phosphate levels while on BGJ398 but have not had a complete metabolic response at the end of the 24 weeks of study drug may be considered for drug continuation in the extension phase, described in 3.1.3. Those who have not responded, have experienced significant side effects, or do not want to continue in the extension phase, will be terminated from the study and referred for other treatment.

During the active drug study period, subjects will not receive calcitriol and phosphorous supplements. However, subjects may be placed on calcitriol and phosphorous while in the post-BGJ398 drug monitoring phase or during dose interruptions, as clinically indicated. During the post-drug monitoring period calcitriol and phosphorous will be re-started on individual basis as clinically indicated (muscle weakness, bone pain, hypophosphatemia).

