### **6.3.2 Methods for Evaluation of Measurable Disease**

All baseline evaluations will be performed as closely as possible to the beginning of treatment and never more than 1 week  $\pm$  4 days before the beginning of the treatment.

The labs done in between NIH visits will be done at the patient's local laboratories; at these local laboratories, only C-terminal FGF23 will be measured as intact FGF23 is not commercially available. Both intact and C-terminal FGF23 levels will be measured by ELISA (Immutopics, Athens, OH and Mayo Medical Laboratories, Rochester, MN) after each NIH visit. We will compare the off-drug levels of FGF23 and blood phosphorous levels with that of baseline levels for evaluating the efficacy of the drug.

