The biochemical measure of disease secondary endpoints will be analyzed using repeated measures mixed models with the contrast of primary interest between the baseline and the 12-week follow-up visit. Additional post hoc comparisons with corrections for multiple comparisons will compare the measures at the end of each cycle to baseline. Of primary interest will be the reduction of FGF23 concentrations, the increase in both plasma phosphorus and 1,25-OH2-vitamin D, and the other biochemical parameters. These concentration endpoints will be log-transformed if appropriate. The muscle-strength testing, SF-36, and PROMIS will also be analyzed using repeated measures mixed models similarly to the biochemical measures of disease. Patients without baseline values for a particular biochemical measure will be excluded from the analysis. Missing values other than baseline measures will be adjusted-for within the repeated measures, mixed model using restricted maximum likelihood techniques.

Radiographic evidence of TIO will be summarized in patient listings.

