### 8.5 SAMPLE SIZE JUSTIFICATION

The sample size of 10 is based upon the highest enrollment that can be reasonably expected. Tumor-induced osteomalacia (TIO) is a very rare neoplastic syndrome; it is expected that only 10 patients will be found within the recruitment period and population that are eligible for enrollment.

The primary study endpoint is the complete metabolic response rate with its 95% confidence limit (95% CL). Patients withdrawing for any reason any time after receiving their first dose of study drug will remain in the ITT population and be counted as a treatment failure. Table 8.4 lists the resulting exact 95% CL for each of the possible response rates for sample sizes of 9 and 10. It is hypothesized that BGJ398 will be effective therapy in 40-60% of the subjects, based on the previous observation that 40-60% of TIO tumors harbor the fibronectin-fibroblast growth factor receptor-1 (FN1/FGFR1) fusion gene. A 60% complete response rate at N=10 would result in a lower 95% confidence bound of 26%. A lower 50% complete response rate at N=10 would still give a lower 95% confidence bound of 18.7% for the complete response rate. Finally, if the target population could not be reached with the final sample size being just 9 and with only 5 of 9 patients having a complete response (55.5%), the lower bound of the 95% CL for the complete response rate would be 21.1%. All three of these lower 95% CL boundaries of the complete response rates: 18.7, 21.1, and 26.2%, could justify BGJ398 therapy for patients with TIO depending on the risks relating to toxicity.

Table 8.4. Listing of the exact 95% confidence limits that would be obtained for each possible complete response rate with study's sample sizes of 9 and 10. The exact 95% confidence limits are based upon the binomial distribution.

Sample Size N=10		Sample size N=9	
Complete Response Rate (%)	Exact 95% CL* (%)	Complete Response Rate (%)	Exact 95% CL* (%)
0	(0.00, 30.8)	0.0	(0.00, 33.6)
10	(0.25, 44.5)	11.1	(0.28, 48.3)
20	(2.5, 55.6)	22.2	(2.8, 60.0)

Abbreviated Title: BGJ398 in TIO  
Version Date: 21MAY2019

30	(6.7, 65.3)	33.3	(7.5, 70.1)
40	(12.2, 73.8)	44.4	(13.7, 78.8)
50	(18.7, 81.3)	55.6	(21.1, 86.3)
60	(26.2, 87.8)	66.7	(29.9, 92.5)
70	(34.8, 93.3)	77.8	(40.0, 97.2)
80	(44.4, 97.5)	88.9	(51.8, 99.7)
90	(55.5, 99.8)	100.0	(66.4, 100.0)
100	(69.2, 100.0)		

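### The main biochemical contrast (baseline versus week 36) rests on patients selected by off-drug FGF23 and phosphate, so it can misstate the all-patient off-drug change, in a direction set by how the others behave on drug

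*Combined protocol and SAP*

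**What the plan says.** Section 8.4 specifies "repeated measures mixed models with the contrast of primary interest between the baseline and the 12-week follow-up visit" for the biochemical endpoints, on both the intent-to-treat and per protocol populations. On missing data it says "Missing values other than baseline measures will be adjusted-for within the repeated measures, mixed model using restricted maximum likelihood techniques". Patient-reported outcomes and strength follow the same model: "The muscle-strength testing, SF-36, and PROMIS will also be analyzed using repeated measures mixed models similarly to the biochemical measures of disease". Section 6.3.2 adds the aim: "We will compare the off-drug levels of FGF23 and blood phosphorous levels with that of baseline levels for evaluating the efficacy of the drug".

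Who has off-drug values is set elsewhere. In section 3.1, "patients who appear to have had a complete metabolic response will be evaluated at the NIH every 4 weeks for 3 additional visits", and complete metabolic response means normal phosphate and FGF23 after drug withdrawal. Section 6.3.4 gives the further 11 weeks to patients in complete response at the end of the 1-week draw period. Sections 3.1.3 and 6.3.4 offer the others the extension (back on BGJ398, if phosphate had normalised on drug) or referral, at that point or whenever response is lost. Section 3.1 says that patients who have not responded, have significant side effects or decline the extension "will be terminated from the study and referred for other treatment".

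Section 3.4 schedules up to 7 daily draws after the last dose. Section 8.4 does not say whether they enter the mixed model, what happens to values taken after BGJ398 is resumed, or which covariance structure is used.

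**The concern.** A REML mixed model handles missing values well when the data that drive missingness are in the model and the covariance is adequate. Here missingness at week 36 is driven by FGF23 and phosphate in the week after the last dose and at later off-drug visits. For a patient not followed, the model as described may hold only baseline and on-drug values. It then projects that patient to week 36 from values that may say little about the off-drug state.

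The resulting mean would be reported under an intent-to-treat label while describing mainly patients who did well off drug. At the response rates hypothesised in section 8.5, that is about 4 to 6 of 10 patients.

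**Working it through.** **Plan's own figures.** The documents give no effect size, SD or correlation for the biochemical contrast, so there is no figure to reproduce. Section 8.5 supplies N = 10 and the response rate: "It is hypothesized that BGJ398 will be effective therapy in 40-60% of the subjects".

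**Step 1: how many are present at week 36.** With presence equal to complete response, the expected number is 10 × 0.4, 0.5 or 0.6 = 4, 5 or 6. From the binomial, P(3 or fewer) = 0.382, 0.172 and 0.055.

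**Step 2: direction.** Let p be the share followed. Let the off-drug gap and on-drug gap be the differences in log change between patients followed and not followed. A random-intercept model projects a patient not followed from the average level over weeks 0-24, which is 13 visits, 12 of them on drug. Roughly,

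bias ≈ (1 − p) × [off-drug gap − (12/13) × on-drug gap].

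Assume that complete responders fall 75% on drug and hold it (ln 0.25 = −1.386), and that the others return to baseline off drug. The off-drug gap is then −1.386. At p = 0.5 the true log change is 0.5 × −1.386 = −0.693, a 50% reduction.

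- Others fall 70% on drug: on-drug gap = −1.386 − ln 0.30 = −0.182. Bias ≈ 0.5 × (−1.386 + 0.168) = −0.609. Estimate = 1 − exp(−1.302) ≈ 73%.
- Others do not change on drug: on-drug gap = −1.386. Bias ≈ 0.5 × (−1.386 + 1.280) = −0.053. Estimate = 1 − exp(−0.746) ≈ 53%.
- Others rise 50% on drug: on-drug gap = −1.386 − ln 1.5 = −1.792. Bias ≈ 0.5 × (−1.386 + 1.654) = +0.134. Estimate = 1 − exp(−0.559) ≈ 43%.

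The sign thus depends on on-drug behaviour in patients not followed.

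**Step 3: simulation.** Assumptions: N = 10; log FGF23 every 2 weeks to week 24, then weeks 28, 32 and 36; between-patient SD 0.5, residual SD 0.3; visit as a factor; random intercept; REML; weeks 28-36 present only for complete responders; trials with no responder discarded. True reduction = 1 − exp[c·ln 0.25 + (1 − c)·r·ln(1 − d)], with c = CR/(1 − (1 − CR)^10), where CR is the complete response rate, d the on-drug fall in the others and r the share of log effect they keep. With r = 0 this gives 42.8, 50.0 and 56.5%.

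| Patients not followed | Estimated week-36 FGF23 reduction, %, at 40/50/60% response | True, % | 95% CI contains truth, % |
|---|---|---|---|
| (a) 70% fall on drug, full rebound | 73/73/73 | 43/50/56 | 5/12/22 |
| (b) 70% fall, half the log effect kept | 72/73/73 | 60/63/66 | 52/57/68 |
| (c) 50% fall, full rebound | 63/66/68 | 43/50/56 | 38/49/57 |
| (d) 35% fall, full rebound | 58/61/64 | 43/50/56 | 72/74/78 |
| (e) no change on drug | 46/52/58 | 43/50/56 | 96/97/96 |
| (f) 50% rise, return to baseline | 34/43/51 | 43/50/56 | 94/96/97 |

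Cases (a) to (e) use 1,000 trials per cell. Case (f) uses fewer, and repeat runs differ by about a point. Phosphorus was not simulated.

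**Step 4: does adding the 1-week draw to the model cure week 36?** In case (a) at 40/60% response, the random-intercept estimate becomes 71.2/72.4% against a true 42.8/56.5%, so it does not. With normally distributed patient effects (true 55%), an unstructured covariance in a very large sample does remove the bias: 55.1/55.0% with the draw, 75.0/69.2% without it. But 17 time points (13 to week 24, the 1-week draw, and weeks 28, 32 and 36) need 17 × 18/2 = 153 covariance parameters, which 10 patients cannot support. At N = 10 with a random intercept the same setting gives 69.6/65.3% with the draw.

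**The case against.** A reader might infer that the contrast overstates the effect as a rule. For FGF23 the documents do not support that. Section 11.1.2 reports that BGJ398 raised FGF23 as well as phosphorus in animals, as an on-target effect, and case (f) shows that such a rise in patients not followed produces understatement. On the other side, section 1.2 describes two TIO patients whose FGF23 fell on drug, so a fall is also plausible. For phosphorus the case for overstatement is clearer: section 1.2 reports a rise on drug even in tumours that do not produce FGF23, and sections 3.1 and 3.1.3 expressly provide for patients with normal phosphate on drug but no complete response off it.

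A reader might also infer that only complete responders are seen at week 36. That is too absolute. The extension is only offered, section 3.1 allows calcitriol and phosphorus to be restarted for hypophosphataemia during off-drug monitoring, and the Précis, section 6.3.3.3 and the schedule read as if everyone has three months off drug. The selection is strong but not exact.

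It can fairly be said that these are secondary/exploratory endpoints in a 10-patient single-arm study, and that the week-36 response rates, with missing counted as failure, will stand beside the mean. That limits the priority. It does not make the mean an all-patient estimate.

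**Conclusion.** The concern holds in conditional form. As an estimate of the all-patient off-drug change, the baseline-to-week-36 contrast can be biased, because follow-up is selected mainly on the outcome and the plan does not say that the deciding draws are modelled.

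The documents do not give the size. Under the stated assumptions it runs from an estimate about 1.7/1.5/1.3 times the true FGF23 reduction (case a), through almost none (case e), to understatement by about 5 to 9 percentage points (case f). These figures depend on assumed effects and SDs and on a random-intercept structure that the plan does not name.

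The primary endpoint (section 8.3) and the response rates in section 8.4 are not affected, because missing status counts as failure. The end-of-cycle analyses ("Additional post hoc comparisons with corrections for multiple comparisons will compare the measures at the end of each cycle to baseline") are less exposed but not immune: section 3.10.1 removes patients whose phosphorus stays low at the maximum tolerated dose on two consecutive cycles. For SF-36, PROMIS and strength the selection is the same, but nothing here indicates its size.

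**What to change.** SAP wording only, with no change to patient management:

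1. Report baseline versus the end of the 1-week off-drug draws (section 3.4) as an all-patient contrast beside week 36. State that it does not show durability and does not remove the week-36 bias. In case (a) it recovers 42.8/50.9/56.5%. If rebound is only half complete at 1 week, it shows 60/63/66% where the week-36 truth is 43/50/56%. Patients who stop before week 24 may have no such draw.
2. Label all week 28-36 results, including SF-36, PROMIS and strength, 'patients remaining in off-drug follow-up'. Give n at each visit, the number in complete response and the number on calcitriol or phosphorus supplements. This label stays correct for a patient whose week-36 visit itself shows relapse.
3. Exclude values taken after BGJ398 is resumed from off-drug contrasts.
4. Add a week-36 sensitivity analysis for FGF23 and phosphorus that sets patients not followed off drug to their own baseline. It matches the truth in case (a) and is conservative if some effect is kept (case b: 43/50/56% against 60/63/66%). Flag or exclude phosphorus and 1,25-(OH)2 vitamin D values taken on supplements.
5. Prespecify a simple covariance structure that 10 patients can support.
6. Reconcile the Précis, section 6.3.3.3 and the schedule with sections 3.1, 3.1.3 and 6.3.4 on who has off-drug values at 9 months.

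The cost is a little more analysis and possibly a less favourable week-36 figure. The draws are already scheduled.

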### 3.1.2 Dose Escalation

The starting dose of BGJ398 for all subjects not previously treated with BGJ398 will be 75 mg. This dose was based on studies investigating this drug's use in subjects with cholangiocarcinoma, as well as our two patients with TIO who have been treated on Novartis' signature trial. Patients previously treated with BGJ398 will be started on the last dose that they were taking prior to enrolling in this study, based on prior tolerability. While the two NIH patients treated on the Novartis Signature trial (6-9) were treated with 3 weeks on BGJ followed by 1 week off BGJ per cycle, our observations that hyperphosphatemia did not develop in these two subjects suggest that continuous BGJ therapy may be more efficacious in this population. Therefore, subjects will be treated with continuous BGJ398 therapy for six 28-day cycles. FGF23 levels will be measured every 2 weeks. If the FGF23 levels are not suppressed to less than 100 RU/ml on the 6-week outpatient labs, the dose of BGJ398 will be increased to 100 mg once daily after the 8-week NIH visit. The increased dose (100 mg) will be maintained for next 8 weeks. If the FGF23 levels continue to be greater than or equal to 100 RU/ml on the 14-week outpatient labs, the dose of BGJ398 will be increased to 125 mg daily after the-16 week NIH visit for the next 8 weeks. If a subject experiences a significant toxicity (DRAE), the medication will be held and restarted at the previous dose as described in section 3.1.1.

Sample dose modification table:

Dose Escalation Schedule	
Dose Level	Dose of BGJ398
Level 1	75 mg
Level 2	100 mg
Level 3	125 mg

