### 3.5 QUESTIONNAIRE

#### **RAND® Medical Outcomes Short Form Survey Instrument (SF-36) Version 1.0**

RAND Medical Outcomes Short Form Survey Instrument (SF-36) Version 1.0 will be used as a secondary outcome measure to determine effects of BGJ398 on Health-Related Quality of Life (HRQOL) over the duration of the study. The RAND® 36-Item Health Survey is a generic validated instrument used to measure (HRQOL) parameters of physical and mental health across age, disease, and treatment groups in individuals 18 years and older. The questionnaire is a multi-purpose self-reported health assessment tool composed of 36 questions in eight different domains that examine aspects of physical and mental health from the patient's point of view. This short questionnaire will be administered in paper or electronic form and completed by the patients at baseline and then monthly for the duration of the study. The average duration of time for completion of the questionnaire is 5-10 minutes. Completed paper versions of the survey will be coded with the subject number and kept in a binder in a locked office. Data collected by means of an electronic tablet

*Abbreviated Title: BGJ398 in TIO*  
*Version Date: 21MAY2019*

	Prescreen	Screen	V0	V 1	V 2	V 3	V 4	V 5	V 6	V 7	V 8	V 9	V 10	V11	V12	V13	V 14	V 15	V 16	V1 7	V 18
Target Date (weeks)		(-)0-6	0	2	4	6	8	10	12	14	16	18	20	22	24	26	28	30	32	34	36
Visit Window (days)		±4	± 4	± 4	± 4	± 4	± 4	± 4	± 4	± 4	± 4	± 4	± 4	± 4	± 4	± 4	± 4	± 4	± 4	± 4	± 4
FGF23 (Mayo)		X	X	X	X	X	X	X	X	X	X	X	X	X	X		X		X		X
BGJ398 - PK Testing			X		X		X														
Urine testing																					
Urine every 2 hours (± 20 minutes) for Pi and Creatinine			X																		
Spot urine Pi, Ca, creatinine				X		X		X		X		X		X	X §						
Urine Pregnancy test (if indicated)		X	X		X		X		X		X		X		X		X		X		X
Urinalysis		X	X		X		X		X		X		X		X		X		X		X
24-hour Ca, Pi, creatinine		X	X		X		X		X		X		X		X		X		X		X
Consults and imaging testing																					
Ophthalmology evaluation (monthly while on BGJ398)			X		X		X		X		X		X		X						X
Nuclear medicine studies (if not done in last 6 mos – repeated at 24 weeks in those with identified tumors)		X													X						
Electrocardiogram (every 4-12 weeks as indicated)		X																			
Echocardiography			X				X								X						
US kidney			X												X						

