### **6.3.3.3 Evaluation of Best Overall Response**

Best overall response is determined in terms of FGF23 levels and blood phosphorous levels at the end of 9 months (6 months on drug and 3 months off the drug).

Complete Response (CR): Normal FGF23 and phosphorous levels are considered as complete metabolic response (CR).

Non-CR/Non-PD: Off drug decrease in FGF23 levels by 50% but still greater than the upper limit of the normal range and increase in plasma phosphorous levels by 50% but not to the normal range is considered as partial metabolic response.

Progressive Disease (PD): Increase in FGF23 levels, and decreased phosphorous levels (compared to that of baseline), off the drug is considered a progressive disease.

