## **8.3 STATISTICAL ANALYSIS OF THE PRIMARY OBJECTIVE AND ENDPOINT**

The primary objective is to induce a complete metabolic response in subjects with tumor-induced osteomalacia (TIO) with BGJ-398. The primary endpoint, complete metabolic response, is defined as the percent of patients in the ITT Population achieving both normal FGF23 and phosphorus levels in the blood at the end of the 12-week follow-up period. The complete response rate will be reported with its exact 95% confidence limits. Patients that for any reason are missing their response status will be counted as failures with respect to achieving complete response.

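### For quality of life and muscle strength, Section 8.4 leads with an off-drug persistence contrast at week 36, which will rest mainly on responders, and leaves the on-treatment comparison at week 24 among six corrected post hoc tests.

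*Combined protocol and SAP*

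**What the plan says.** - **Objective.** Section 1.1.2 asks for the effects of BGJ398 on mineral homeostasis, quality of life and muscle strength. Table 1 ties the primary endpoint to levels measured off study drug, but puts no such condition on quality of life or strength. Section 3.5 says the SF-36 "will be used as a secondary outcome measure to determine effects of BGJ398 on Health-Related Quality of Life (HRQOL", and places this over the whole course of the study.
- **Lead contrast.** Section 8.4 analyses the biochemical measures by mixed model "with the contrast of primary interest between the baseline and the 12-week follow-up visit". It then adds: "The muscle-strength testing, SF-36, and PROMIS will also be analyzed using repeated measures mixed models similarly to the biochemical measures of disease". It states no separate contrast for these scales.
- **Timing of that visit.** Section 8.3 places the primary endpoint "at the end of the 12-week follow-up period", and Section 6.3.3.3 judges best response "at the end of 9 months (6 months on drug and 3 months off the drug". The visit is week 36.
- **On-drug comparisons.** Section 8.4: "Additional post hoc comparisons with corrections for multiple comparisons will compare the measures at the end of each cycle to baseline". The correction method is not named. Section 3.1.2 fixes the number of cycles: "subjects will be treated with continuous BGJ398 therapy for six 28-day cycles".
- **After week 24.** Under Section 3.1, the three further monthly visits are for apparent complete metabolic responders. Under Sections 3.1.3 and 6.3.4, a patient without complete response after the one-week washout, or who loses it later, may be offered resumed BGJ398 or referred elsewhere. Section 3.1 also says: "During the post-drug monitoring period calcitriol and phosphorous will be re-started on individual basis as clinically indicated".
- **Six-minute walk.** Section 8.4 lists it as a secondary endpoint (baseline, weeks 24 and 36), but the analysis text does not name it.

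**The concern.** The question asked and the contrast given first place do not match. Baseline against week 36 shows whether a gain outlasts the drug. The secondary objective is about what BGJ398 does to quality of life and strength, and 24 of the 36 weeks are on drug. A patient could feel and move better throughout treatment and lose the gain after withdrawal; the lead contrast would not show it, and the reader would have to find it among the corrected cycle-end results.

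The week-36 contrast is also a poor base for a lead result. Whether a patient is still under off-drug observation then depends on biochemical response, and some who are observed may have restarted calcitriol and phosphate. Restricted maximum likelihood, which 8.4 relies on for missing values, needs the gaps to be explained by what is in the model. Biochemical response decides who stays, and it is not stated to be in the quality-of-life or strength models.

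**Working it through.** **1. The plan's own figures.** Section 8.5 gives exact limits for the complete response rate only. They reproduce: 5/10 gives 18.7% to 81.3%, 6/10 gives 26.2% to 87.8%, and 5/9 gives a lower limit of 21.2% (21.1% stated, a last-digit difference). The plan gives no alpha, SD, effect size or power for quality of life or strength, so everything below is illustrative.

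**2. Inputs.**
- N = 10 (Section 8.5).
- Six cycles of 28 days: 6 × 28 = 168 days = 24 weeks, so the sixth cycle-end comparison is week 24 (Section 3.1.2).
- Strength, SF-36 and PROMIS at baseline and every 4 weeks (Sections 3.5 and 8.4), so week-24 data are planned.
- Assumed: two-sided alpha 0.05, Bonferroni over six comparisons, and standardized changes d (mean change divided by SD of change) of 0.8, 1.0 and 1.2.

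**3. Why a correction is reasonable.** Six uncorrected independent tests would carry a familywise error of 1 − 0.95^6 = 26.5%. The cost arises because no single on-drug contrast is set apart.

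**4. Cost of the correction at week 24.** Paired t-test with n − 1 = 9 df and noncentrality d√n. For d = 1.0 this is √10 = 3.16. The critical value is 2.26 at 0.05 and 3.36 at 0.05/6 = 0.0083.

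| d | Power at 0.05 | Power at 0.0083 |
|---|---|---|
| 0.8 | 62% | 28% |
| 1.0 | 80% | 47% |
| 1.2 | 92% | 66% |

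The change detectable with 80% power rises from 1.00 SD to 1.37 SD.

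**5. Sensitivity to the assumed method (d = 1.0).**
- Max-t correction, 9 df: 54% if the six contrasts correlate 0.5, and 62% if they correlate 0.8.
- Pooled mixed model with about 54 residual df: 87% uncorrected, 66% with Bonferroni, about 69% to 75% with max-t.

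The loss is therefore 33 points in the simplest case (80 − 47) and roughly 12 to 21 points under the pooled model (87 − 75 to 87 − 66).

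**6. Who is left at week 36.** Section 8.5 hypothesizes that treatment is effective in 40% to 60% of patients. If that fraction has complete response and stays in follow-up, 0.4 × 10 to 0.6 × 10 gives 4 to 6 patients. Power for a 1.0 SD change at 0.05, using only their paired data:

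| Patients at week 36 | Power | Change detectable with 80% power |
|---|---|---|
| 4 | 29% | 2.13 SD |
| 5 | 40% | 1.68 SD |
| 6 | 51% | 1.43 SD |

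The mixed model also uses earlier visits of the other patients, so it may do somewhat better, but only by relying on the missing-data assumption questioned above. None of these figures allows for the selection of responders.

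**The case against.** The case for leaving the plan alone has real weight.

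- **Durable benefit is what the trial is built around.** The primary endpoint is off drug, Section 1.2 speaks of a possibly tumoricidal effect, and Section 6.3.2 judges efficacy by comparing off-drug levels with baseline. A reader might infer that week 36 says nothing about the effect of BGJ398. The documents do not support that: it measures persistence of benefit, which is an effect of the drug, though not the on-treatment effect.
- **The on-drug comparison is already planned.** Although labelled post hoc, the cycle-end comparisons are specified in advance. Week-24 estimates will exist, and a gain that fades would be visible in them. It would be wrong to say the on-treatment effect goes unexamined.
- **The link is one word.** Similarly may carry over only the model type. In that case no lead contrast is stated for these scales, which also needs settling.
- **Supplements.** A reader might infer that a gain from restarted calcitriol and phosphate would pass for a drug effect. This is weak. Under Section 4.2.4 patients take these agents until 3 days before the first dose, so restarting them largely returns patients to their pre-baseline therapy. Week 24 is not wholly free of them either, since Section 3.1 allows them during dose interruptions.
- **Not everyone is off drug at week 36.** Some will have resumed BGJ398. This blurs the persistence reading further.
- **The power loss depends on an assumed method**, as step 5 shows.

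What stands is that the lead contrast for these scales does not target the on-treatment effect, is thinly and selectively populated, and outranks a better-populated contrast that does.

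**Conclusion.** The concern holds as a mismatch between a secondary objective and the contrast given priority for it. Under the natural reading of 8.4, SF-36, PROMIS and strength lead with persistence at week 36, resting mainly on apparent complete responders. Week 24 is planned but subordinate.

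The size is moderate and illustrative: for a 1.0 SD change in 10 patients, 80% power uncorrected against 47% under Bonferroni with a paired t-test, and a loss of about 12 to 21 points under a pooled model. At week 36, with 4 to 6 patients, power is 29% to 51%. These figures rest on an assumed alpha, effect size and correction, and on the 40% to 60% hypothesis carrying over to follow-up.

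The point should be addressed, but it touches secondary endpoints only. The complete response rate and its exact limits are unaffected.

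**What to change.** In Section 8.4, for SF-36, PROMIS, strength and the six-minute walk:

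1. Name week 24 against baseline as the single lead contrast for each measure, without multiplicity correction.
2. Keep the other cycle-end comparisons corrected, and name the method.
3. Keep week 36 against baseline as a secondary persistence contrast. Report how many patients contribute, and identify those who resumed BGJ398 or restarted calcitriol or phosphate.
4. Name the six-minute walk in the analysis text, with its two post-baseline times.

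This is a wording change using data already scheduled, with no added visits. The price is that the durability contrast loses its lead position for these measures. Two limits remain: dropout before week 24 can still select patients, and one uncorrected contrast per measure does not control error across measures (the eight SF-36 domains alone give eight). The current week-36 lead contrast has that second limit too.
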